Recent studies showed that alternative therapies are used as first aid treatment for burns as Aloe Vera, saliva and a tea tree oil impregnated dressing applied as first aid to a porcine deep dermal contact burn, results of it showed significantly decrease sub dermal temperature within the skin during the treatment period.

Tea tree oil [TTO] (*Melaleuca alternifolia*) is a clear, colorless to pale yellow liquid, and is insoluble in water. It is lipophilic and works through penetrating the skin and mucous membranes. The active ingredients responsible for killing bacteria and fungi in TTO include terpinene-4-ol, alpha-terpineol and alphaphinene, which inhibit cell respiration and disruption of cell membrane permeability with the resultant leakage of potassium.

Inherent in the previous statements, is the belief that there is a need to investigate whether TTO would be more cost effective, enhance rapid healing than the conventional topical agent.

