**Tool I: (Burn patient's assessment sheet)**

This tool will mainly aim to assess burn parameters (as extent, depth, and cause of burn), criteria of wound healing (as wound color, appearance of burn wound, signs of infection and presence of exudates). It will be comprised of three parts.

**Part I: Patient Sociodemographic data:** including:

- Personal characteristics: as Patients' age, gender, level of education, occupation, date of burn, date of admission, date of discharge and habits.
- Patient history including past and present history.

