**-Morphological changes of the wound:**

This part will be used to assess burn wound healing, and determine signs of infection including signs of inflammation as wound color, presence of exudates (amount, color, and type), size, depth, edema, as well as frequency of dressing change.

- **Photographic pictures:**

Colored digital photographs will be taken three times to assess wound healing process (day of burn, each other day till healing and after one month)

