## **Method**

1. Written approval will be obtained from the hospital administrator and head of Burn Department, after explanation of the study aim.
2. The study tools will be developed by the researcher after review of relevant literature.
3. The developed tools will be submitted to 5 experts in the fields of plastic surgery &burn and Medical Surgical Nursing to test its content validity and necessary modification will be done accordingly.
4. Reliability of the tool will be tested.
5. Ethical considerations:
  - a. Patient's written informed consent will be obtained after explanation of the study aim.
  - b. Confidentiality, privacy and right of withdrawal will be assured.
  - c. Ethical committee approval will be obtained.
6. Pilot study will be conducted on 5 patients for testing, clarity, feasibility and applicability of the developed tools and modification will be done.
7. The study subjects meeting inclusion criteria and will be sequentially divided into two groups, the first group will receive conventional dressing (control group), and this dressing will be changed routinely once every other day. For the second group the wound will be dressed by TTO, which will be changed every other day till healing occurs. This frequency is advocated, since more frequent dressing change will interfere with granulation tissue formation.
8. All burn wound will be washed gently with Saline, and all open blister and loose non-viable tissue will be removed from the burn, intact blisters will be

left, and then the topical agents will be applied directly on wound. Burns involving body joints will be kept in functional position.

9. Initial assessment of all patients will be done using tool I. Subsequent assessment will be done on 4th, 14th, 21th of topical dressing agents use until the wound healing from both groups using tool II.
10. Colored digital photographs will be taken-if possible- to assess wound healing process at the (day of burn, each other day till healing, after one month)
11. Initial and ongoing assessment results for the conventional dressing, compared to TTO dressings, will be carried out using appropriate statistical methods.

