#### **Statistical Analysis Plan (SAP):**

Data will be analyzed using IBM SPSS software package version 23.0. The Shapiro-Wilk will be used to verify the normality of distribution of variables; Comparisons between groups for categorical variables will be assessed using Chi-square test (Monte Carlo or Fisher Exact). Student t-test will be used to compare two groups for normally distributed quantitative variables, Mann Whitney test will be used to compare two groups for not normally distributed quantitative variables, Friedman Test for multiple comparisons between the different periods in each group. Significance of the obtained results will be judged at the 0.5% level.

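### No time-to-healing outcome is named, and no rule covers patients already healed at the day 14 and day 21 assessments

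*Combined protocol and SAP*

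**What the plan says.** The Introduction gives the motivating question as "whether TTO would be more cost effective, enhance rapid healing than the conventional topical agent". The Aim of the study is broader: it compares the two dressings on the healing of second-degree burns.

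None of the listed data items is a healing date. Tool I, Part I includes "date of burn, date of admission, date of discharge and habits". Tool II lists wound attributes such as colour, exudate, size, depth and edema, plus how often the dressing is changed. Complete healing is not defined.

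Method, item 9 places follow-up on the 4th, 14th and 21st (the word day is missing) "of topical dressing agents use until the wound healing from both groups using tool II".

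Two planned activities could yield a healing date. Item 7 has the TTO dressing, "which will be changed every other day till healing occurs", and the control dressing is changed at the same interval. Tool II schedules photographs on the "day of burn, each other day till healing and after one month", although item 10 makes them conditional on being possible. Neither is linked to an outcome.

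On analysis, item 11 says: "Initial and ongoing assessment results for the conventional dressing, compared to TTO dressings, will be carried out using appropriate statistical methods". For quantitative data the SAP gives a t-test if normally distributed; otherwise "Mann Whitney test will be used to compare two groups for not normally distributed quantitative variables". Over time it gives "Friedman Test for multiple comparisons between the different periods in each group". Categorical variables get chi-square, Monte Carlo or Fisher. There is no rule for patients already healed at a visit.

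**The concern.** A trial motivated by speed of healing should say how speed is measured. Here the nearest measures are wound attributes at three visits. Because both superficial and deep burns up to 10% of body surface are eligible, some patients may well heal before day 14 or day 21.

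Item 9 can be read as ending assessment at healing, or as covering every patient at each visit with healed wounds recorded as such. Two analysts could follow the text and report different day 14 and 21 results. On the first reading, the between-arm test of wound size excludes exactly the patients who did best. If one dressing works faster, that arm loses more of them, so the comparison is between unlike remnants of the two groups. Friedman needs a value at every period, so it would then describe only the slowest healers. On either reading it is a within-group test and cannot compare the arms. Day 4 is essentially unaffected.

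**Working it through.** **What can be reproduced.** The plan gives 50 patients, 25 per group, with no power, effect size, SD or healing rate. There is no figure of its own to reproduce.

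**Inputs.** From the documents: 25 per arm, visits at days 4, 14 and 21, dressing changes every other day, mixed depth, Mann-Whitney. Assumed: healing time T is normal by depth and 5 days shorter on TTO, with a floor of 3 days. Area at day t is A(t) = A0 × (1 − t/T), or 0 once healed, with A0 uniform on 2-10. Healing is seen on a 2-day grid. Patients unhealed after day 30 are censored (log-rank) or ranked last (Mann-Whitney). Tests are two-sided at 5%.

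**Step 1: open wounds at each visit.** The main scenario has half deep burns, with control means of 13 days (SD 3) superficial and 21 days (SD 4) deep. The TTO means are 8 and 16.

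- Day 14, control: P(open) = ½[1 − Φ((14−13)/3)] + ½[1 − Φ((14−21)/4)] = ½(0.369 + 0.960) = 0.665; × 25 = 16.6.
- Day 14, TTO: ½[1 − Φ((14−8)/3)] + ½[1 − Φ((14−16)/4)] = ½(0.023 + 0.691) = 0.357; × 25 = 8.9.
- Day 21, by the same formula: control ½(0.004 + 0.500) × 25 = 6.3; TTO ½(0.000 + 0.106) × 25 = 1.3.

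In 61% of such trials fewer than two TTO wounds are still open at day 21.

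**Step 2: day-14 power on raw area, in percent** (3000 simulated trials per row; simulation error at most √(0.25/3000) = 0.9 points).

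| Assumed control healing time, days | Open only | Healed = 0 | Days to healing, Mann-Whitney | Days to healing, log-rank |
|---|---|---|---|---|
| Main | 12 | 65 | 87 | 83 |
| As main, deep mean 17 | 7 | 88 | 99 | 97 |
| As main, 75% deep | 31 | 76 | 89 | 92 |
| As main, 25% deep | 3 | 68 | 96 | 89 |
| Half deep, 16 (SD 4) and 25 (SD 5) | 12 | 61 | 73 | 69 |
| All deep, 21 (SD 4) | 61 | 93 | 99 | 98 |
| All deep, 24 (SD 5) | 44 | 70 | 91 | 89 |
| All deep, 28 (SD 5) | 38 | 44 | 92 | 91 |
| All deep, 28 (SD 8) | 19 | 31 | 54 | 52 |

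Allowing for variation between repeat runs, the mixed-depth range is about 3-33% against 61-88%. With no true effect, all tests rejected in 3-6% of trials. At the 0.5% level written in the SAP, the main row becomes 1, 31, 55 and 54.

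**Step 3: does the metric matter?** Raw area carries the spread in baseline size. With area as percent of baseline, the four all-deep rows give open only against healed = 0 of 86/99, 80/92, 89/91 and 40/56. The relative losses are 1 − 86/99 = 13%, 1 − 80/92 = 13%, 1 − 89/91 = 2% and 1 − 40/56 = 29%; a repeat run gave about 3-27%. On this metric the day-14 snapshot with healed = 0 roughly matches days to healing (Mann-Whitney/log-rank): 99 against 99/98, 92 against 92/90, 91 against 91/89, 56 against 52/52. In the main mixed scenario days to healing stays ahead, 87/84 against 69.

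**Step 4: day 21.** In the mixed scenarios, power is 0-7% with open wounds only (9% at most in a repeat run) against 11-77% with healed = 0. A different model (lognormal healing times, percent of baseline) with slow medians of 24 and 18 days gives 20% against 85% (CV 0.3) and 14% against 63% (CV 0.4). Its day-14 figures are 74% against 91% and 44% against 70%.

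**Step 5: size of the difference.** In the main scenario, the mean difference in percent area remaining at day 14 is 6.6 points among open wounds and 10.6 among all patients. At day 21 it is 4.4 against 2.7. The selected comparison does not err in one consistent direction.

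**The case against.** A reader might infer that the plan discards healed patients and so loses most of its power. The documents do not support that. Item 9 does not say later values are blank, item 11 excludes nobody, and photographs are planned one month on, so observation past healing is foreseen where possible. The text leaves the matter unspecified, and the low power figures belong to one of two possible readings.

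A reader might also infer that the listed tests are wrong, or that a survival method is essential. Neither follows. With healed patients kept, the t-test and Mann-Whitney comparisons are valid, and the SAP's chi-square or Fisher test could be applied to healed by a given day. Under the same assumptions, Fisher at day 14 had 46-80% power in the mixed scenarios, against 4-32% for open wounds only in that run. It was weaker with slow, all-deep healing: 62% at a mean of 21 days, otherwise 0-14%. The plan does not name that variable, but the test is there.

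Nor is days to healing always more powerful. The all-deep results on percent of baseline show rough parity.

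Finally, the aim is healing in general, with speed appearing only in the Introduction beside cost, and several Tool II items are not plainly quantitative. That makes the choice of days to healing as primary partly a judgement. It does not supply the missing rule for healed patients.

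**Conclusion.** Two omissions stand on the text alone: healing speed is not turned into an outcome, and no rule covers patients healed before a visit. The consequence is conditional. If healed patients have no value, wound-size comparisons at days 14 and 21 are selected on the outcome. The day-14 power loss is then severe with mixed depth. With slow, all-deep healing it is modest on percent of baseline, while day 21 still falls clearly. If healed patients are kept, the listed tests serve.

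Every healing time, depth mix and effect used here is assumed, since the documents give none, and the power figures concern wound size only. They show the direction and possible scale of the loss and do not predict it for this trial. This is a cheap improvement that removes a real ambiguity.

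**What to change.** 1. Define complete healing and record its date at the every-other-day dressing changes already planned.
2. Make days from first study dressing to complete healing the primary outcome.
3. Name one between-arm test in advance. Log-rank, with unhealed patients censored at last observation, also accommodates patients who leave early, provided leaving is unrelated to how soon they would heal. Mann-Whitney, already listed, works with unhealed patients ranked last if all are followed to the same day.
4. State that patients healed before day 14 or 21 stay in those analyses as healed, with size 0.
5. Label Friedman as descriptive within group.

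The cost is one data field, which can be added while the tools are piloted and modified (Method, item 6), and a few SAP sentences. SPSS provides both tests. The drawbacks are slightly more data entry and a healing date accurate only to about 2 days. No new patients, visits or procedures are needed.

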### **Aim of the study**

Compare the effect of two topical dressing techniques on the healing of second degree burn wounds; *melaleuca alternifolia* (tea tree oil) and conventional dressings.

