**Patient's inclusion criteria will include:**

- Adults of both genders (18-60 years), able and willing to cooperate and communicate.
- Newly admitted to the study setting with recent 2nd degree burns whether superficial or deep ≤10%TSBA.
- Free of associated illness that affect wound healing as DM, immune disorder, or associated injuries.
- Free from pre-existing skin conditions such as eczema

**Tools:** Two tools will be used on this study:

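### The plan sets no value for a wound that has already healed, so the day 14 and day 21 comparisons of the dressings may leave out the best outcomes

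*Combined protocol and SAP*

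**What the plan says.** - **Aim of the study:** "Compare the effect of two topical dressing techniques on the healing of second degree burn wounds". The question is a between-dressing one.
- **Inclusion criteria:** second-"degree burns whether superficial or deep" are eligible, so healing times within an arm may vary widely.
- **Method, item 9:** Tool I is used at baseline. Tool II follows at the 4th, 14th and 21st, "until the wound healing from both groups using tool II". No unit is printed; I read these as days.
- **Method, item 10:** photographs, if possible, on the day of burn, "each other day till healing, after one month".
- **Method, item 11:** "Initial and ongoing assessment results for the conventional dressing, compared to TTO dressings, will be carried out using appropriate statistical methods".
- **SAP:** chi-square (Monte Carlo or Fisher), t and Mann-Whitney tests are assigned by type of variable, for example "Mann Whitney test will be used to compare two groups for not normally distributed quantitative variables". None is tied to a Tool II item or visit. The only method across time points is "Friedman Test for multiple comparisons between the different periods in each group". The level is given in "Significance of the obtained results will be judged at the 0.5% level".

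Tool II lists color, exudate (amount, color, type), size, depth, edema and frequency of dressing change. It has no item for a healed wound. No section defines healed or says what is entered for a healed wound at later visits.

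**The concern.** Healing is the outcome, and item 9 makes healing the end of assessment. If Tool II is not completed after a wound has closed, the patients who did best have no value at day 14 or day 21. The tests at those visits then compare only the wounds still open. The faster dressing loses more patients, and those it keeps are its slowest healers, so a real advantage is diluted.

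The Friedman test does not repair this. It is run within each arm, so it says nothing about the difference between dressings. It also uses only patients with a value at every period, so early healers drop out of it too.

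At stake is a missed effect in a trial of 25 per arm. A second, smaller matter is that item, visit and coding could all be chosen after the data are seen.

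**Working it through.** The plan gives no power, effect size or healing time, so there is no figure of its own to reproduce. What follows is illustration on assumed inputs.

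**Inputs from the documents.** 25 patients per arm; visits 4, 14 and 21; burns up to 10% of body surface; level 0.5% as written.

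**Assumed inputs.** Healing time T log-normal with log-SD 0.4; medians control/TTO 16/12, 20/14 or 20/16 days; initial size S uniform on 2 to 10% TBSA; linear shrinkage, size(t) = S × max(0, 1 − t/T); two-sided Mann-Whitney, 4,000 simulated trials. Results at 5% are shown beside the written 0.5%.

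**Step 1. Patients still open at a visit.** Expected number = 25 × Φ(ln(median/visit)/0.4).

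- Median 16, day 14: ln(16/14)/0.4 = 0.334, Φ = 0.631, so 15.8 patients.
- Median 12, day 14: ln(12/14)/0.4 = −0.385, Φ = 0.350, so 8.7 patients.

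| Medians | Day 4 | Day 14 (control, TTO) | Day 21 (control, TTO) |
|---|---|---|---|
| 16/12 | about 25 each | 15.8, 8.7 | 6.2, 2.0 |
| 20/14 | about 25 each | 20.3, 12.5 | 11.3, 3.9 |
| 20/16 | about 25 each | 20.3, 15.8 | 11.3, 6.2 |

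Day 4 is unaffected. From day 14 the loss is unequal between arms.

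**Step 2. Day-14 Mann-Whitney power for wound size.**

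| Medians | 5%: healed = 0 | 5%: healed dropped | 0.5%: healed = 0 | 0.5%: healed dropped |
|---|---|---|---|---|
| 16/12 | 57% | 11% | 24% | 1% |
| 20/14 | 77% | 24% | 42% | 4% |
| 20/16 | 38% | 14% | 12% | 2% |

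A rerun with separate code and a new seed agreed within simulation error.

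**Step 3. A milder reading.** Suppose the first visit at which the wound is seen healed is recorded and only later visits are lost. Day 14 is then essentially intact. Day-21 power at 5% still falls from 37% to 10% (16/12), 67% to 29% (20/14) and 34% to 16% (20/16).

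**Step 4. Identical arms.** With medians 16/16 and 20/20, day-14 rejection at 5% is 4.4% to 5.4% under either coding.

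**Step 5. Sensitivity.** For 20/14 at day 14 and 5%, healed = 0 against dropped is 94.6% against 42.5% with log-SD 0.3, and 56.8% against 15.6% with log-SD 0.5. With size as a percentage of initial area, the three scenarios give 59% against 13%, 84% against 35% and 45% against 19%. The size of the loss varies; its direction does not.

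**Step 6. Direction of the estimate.** Assume half the burns are superficial (medians 14/10), half deep, log-SD 0.3. The mean day-14 difference in size, control minus TTO, with healed wounds dropped, depends on the deep-burn medians:

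| Deep medians (control/TTO) | Difference, % TBSA |
|---|---|
| 24/24 | −0.23 |
| 24/22 | about 0 |
| 24/20 | +0.22 |
| 24/17 | +0.56 |

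At 24/24 the same difference with healed = 0 is +0.24.

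**Step 7. What Friedman can show.** In a separate simulation (three visits, independent normal errors), the arms truly differ by 1 SD at the last visit and both change strongly. Friedman is significant in both arms in 99% to 100% of trials, so it does not reveal the difference. Mann-Whitney at that visit detects it in 92% (5%) or 68% (0.5%).

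**Step 8. Unnamed item and visit.** Counting 8 Tool II items at 3 visits gives 24 tests. If they were independent, the chance of at least one false positive would be 1 − 0.95^24 = 71% at 5%, or 1 − 0.995^24 = 11% at 0.5%.

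**The case against.** **The text does not establish that healed wounds are lost.** This stands. Item 9 can also be read as assessing until wounds in both groups have healed, and the one-month photograph shows that some observation after healing is intended. A reader might infer that early healers will certainly be excluded; the documents support only that no rule is stated and that the literal reading excludes them. A photograph taken if possible does not supply a Tool II value.

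**Between-group tests are planned.** This also stands. A reader might infer that the plan never compares the dressings, or relies on Friedman to do so. Neither is right: the SAP names tests for every variable type, item 11 promises comparison of ongoing results, and nothing says Friedman will be used between arms. A within-arm Friedman test as description is acceptable. The missing link to item and visit is under-specification; the healed-wound gap carries the harm.

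**The result might be said to reverse.** A reader could infer this from the mixture of superficial and deep burns. It needs TTO to speed superficial burns and do almost nothing in deep ones: at 24/22 the reversal has gone. Even at 24/24, a result significantly favouring control at 5% occurs in only about 6% of trials. The documents give nothing on effect by depth.

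**All magnitudes rest on assumptions.** True, including linear shrinkage and size as a continuous measure. The loss appears in every scenario with a real difference that was run.

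**Conclusion.** The concern holds as a gap with a definite consequence under the literal reading. Tool II assessment runs until healing, no value is set for a healed wound, and the only across-time method neither compares dressings nor keeps patients with incomplete rows. If healed wounds are dropped, day-14 power at 5% falls by 46, 53 and 24 percentage points in the three assumed scenarios (57 − 11, 77 − 24, 38 − 14). If only visits after the first healed one are lost, day 14 is spared but day 21 is not.

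The harm is a missed effect. It is not an inflated false-positive rate when the arms are identical, and reversal of direction is a special case. The sizes depend on assumed healing times, spread and shrinkage, and on reading the visits as days. The plan should be changed, but it is not without a between-dressing comparison.

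**What to change.** Add to the SAP:

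1. A definition of a healed wound, and a field for the date it is first seen healed at a dressing change, recorded the same way in both arms.
2. A coding rule: from that visit on, the wound is entered as size 0, no exudate, no edema, and 'healed' for the remaining wound items.
3. Patients who leave before healing are missing at later visits, or censored in a time-to-healing analysis. They are not counted as healed. Report their number by arm.
4. The dressings are compared using all available patients, healed wounds included.
5. One main between-dressing comparison is named: either time to healing (log-rank, healing checked at the every-other-day dressing changes) or wound size at day 14 (Mann-Whitney). Give the group difference with a confidence interval whose level matches the significance level once that is settled: 99.5% if 0.5% is meant, 95% if 5% is meant.
6. Other items and visits are supportive. Friedman is descriptive within each arm, and the assessments that form its periods are stated.

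Time to healing fits the aim more closely and avoids assigning sizes to healed wounds. Under the same assumptions, one simulation run gave it 66%, 85% and 48% power at 5%, against 57%, 77% and 41% for day-14 size in that run, a modest gain.

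**Cost.** Some SAP wording, one recorded date and a little more analysis. No new visits are needed, because dressings are already changed every other day; but the plan does not now say that healing is noted then, so the recording must be added. By day 21 there will be many tied zeros. A Fisher test of healed yes/no is easier to read there but weaker (52% against 67% for 20/14 at 5%).

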### **Materials and method**

#### **Materials**

**Design:** An experimental design will be utilized.

**Setting:** The present study will be conducted at the burn unit, Alexandria Main University Hospital, Alexandria, Egypt.

**Subject:** A convenient sample of 50 patients admitted to burn unit suffering from second-degree burns will be included in the present study.

The fifty patients will be sequentially enrolled into two equal groups:-

- The first group (25 patients) will be managed conventional dressings (control group).

- The second group (25 patients) will be managed by local application tea tree oil (study group).

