## **Results**

The collected data will be analyzed, categorized and tabulated, the appropriate correlation and significant test will be done.

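### The plan's only significance level, 0.5%, has no stated basis and costs much of the power at 25 per group; settle it by dated amendment before analysis by group

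*Combined protocol and SAP*

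**What the plan says.** The threshold is the last sentence of the Statistical Analysis Plan section: "Significance of the obtained results will be judged at the 0.5% level". It follows a list of test types. For categorical variables: "Comparisons between groups for categorical variables will be assessed using Chi-square test (Monte Carlo or Fisher Exact"). For continuous variables: "Student t-test will be used to compare two groups for normally distributed quantitative variables", with Mann-Whitney for non-normal data. Within groups: "Friedman Test for multiple comparisons between the different periods in each group". The section does not say whether tests are one- or two-sided, and it does not tie any test to an outcome or visit.

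Other sections bear on the level:

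- **Materials, Subject:** a convenience sample of 50, with "The fifty patients will be sequentially enrolled into two equal groups", 25 in each. No sample-size calculation is given.
- **Tool II, morphological changes:** several wound features are recorded, including "presence of exudates (amount, color, and type), size, depth, edema, as well as frequency of dressing change". None is named as primary.
- **Method, item 9:** follow-up on the 4th, 14th and 21st day "of topical dressing agents use until the wound healing from both groups using tool II".
- **Results:** further testing is left open: "the appropriate correlation and significant test will be done".

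**The concern.** This sentence is the trial's only rule for calling a result significant. It sets a level ten times stricter than 5%, in a trial of 25 per group whose size was not derived from any level. A strict level can be a sound choice, but then a reader expects a reason, such as a correction for several tests, and some acknowledgement of the power given up. The plan has neither.

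Two things are at stake. If 0.5% is followed, a fairly large true benefit would be missed more often than found. If the report uses 5% without a prior correction, it departs from the written plan, and the level could be chosen after the results are known. Every result with p between 0.005 and 0.05 depends on which level is applied.

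**Working it through.** **Inputs from the documents.** Level 0.005 (Statistical Analysis Plan); 25 per group (Materials, Subject); three follow-up days (Method, item 9).

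**Assumptions.** Two-sided tests, because the SAP is silent. The effect sizes are mine, because the plan gives none. 5% serves only as a comparison level and is not in the documents.

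**1. Can 0.5% be rebuilt from the plan?** No. It needs a power, an effect size or a number of tests, and none is stated. Two coincidences should not be over-read:

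- 0.05/10 = 0.005, but the plan states no such division and no set of ten tests.
- By the normal approximation, 80% power at 0.8 SD and two-sided 5% needs 2 × (1.960 + 0.842)² / 0.8² = 24.5, so 25 per group, which is the planned size. No such calculation is in the plan, so this is not evidence of intent.

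**2. Observed difference needed for significance (t-test, 48 df).** t_crit × √(2/25), where √(2/25) = 0.2828:

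- 0.5%: 2.943 × 0.2828 = 0.832 SD
- 5%: 2.011 × 0.2828 = 0.569 SD

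Observed differences between about 0.57 and 0.83 SD are significant at 5% but not at 0.5%.

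**3. t-test power (noncentral t, noncentrality = d / 0.2828, 25 per group).**

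| True difference | Noncentrality | Power at 0.5% | Power at 5% |
|---|---|---|---|
| 0.5 SD | 1.77 | 13.3% | 41.0% |
| 0.8 SD | 2.83 | 46.2% | 79.1% |
| 1.0 SD | 3.54 | 72.0% | 93.4% |

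- Difference detectable with 80% power: 1.076 SD at 0.5%, 0.809 SD at 5%. With 20 analysed per group: 1.217 and 0.909 SD.
- Patients per group for 80% power at 0.8 SD: 43.6, so 44, at 0.5%; 25.5, so 26, at 5%.
- If tests were one-sided, power at 0.8 SD would be 56.2% and 87.4%. The gap remains.

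**4. A yes/no outcome.** Fisher exact test, all tables enumerated, 25 per group, assumed 40% vs 80% healed: power 45.2% at 0.5%, 78.8% at 5%.

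**5. What a flat 5% would do.** The Tool II features can be counted as 6 (colour, exudate, size, depth, edema, dressing frequency) or up to about 10 if exudate is split and infection signs are added. The chance of at least one false positive over k independent tests is 1 − (1 − α)^k:

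| k | α = 0.5% | α = 5% |
|---|---|---|
| 6 | 3.0% | 26.5% |
| 10 | 4.9% | 40.1% |
| 18 (6 items × 3 visits) | 8.6% | 60.3% |
| 30 (10 items × 3 visits) | 14.0% | 78.5% |

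The features and visits are surely correlated, which lowers these figures. For 10 items at one visit with a correlation of 0.5, 40.1% falls to about 29%.

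**The case against.** The strongest reply is that there is no documented error. The SAP gives one level, nothing contradicts it, and it can be applied as written: p between 0.005 and 0.05 is not significant. Low power is a consequence of a strict choice, not a mistake. The phrase about obtained results reads naturally as covering every test. Chi-square and Friedman tests have no direction and the stated aim is a plain comparison, so the silence on sidedness is minor. Most Tool II features look categorical, so SD units may not describe the eventual outcome.

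Much of this stands. A reader might infer that 0.5% is a misprint for 5%. The documents do not support that: no section states 5%, and the suspicion rests on convention alone. A reader might also infer that it is a Bonferroni level for ten tests. That is unsupported too, since the item count is not fixed at ten, and the Friedman tests and the open-ended tests in the Results section fall outside such a count. Nor does an unusual level threaten validity, because a stricter level lowers the false-positive risk.

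What the reply does not answer is why this level was chosen when it costs so much power. The Fisher scenario shows a loss of similar size for a yes/no outcome, so the point does not depend on a continuous endpoint.

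**Conclusion.** The point holds as an unsupported decision threshold, not as an arithmetic error or a proven slip. At 25 per group, two-sided, the written level gives about 46% rather than 79% power at 0.8 SD and about 45% rather than 79% for 40% vs 80% healed. It also moves the difference detectable with 80% power from 0.81 to 1.08 SD. These sizes rest on assumed effects and on all 25 patients per group being analysed; with fewer, both levels do worse. The false-positive figures for a flat 5% rest on independence and on how the Tool II items are counted. The plan should be fixed, but it is not invalid as it stands: the rule is conservative and can be executed.

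**What to change.** Settle the level by dated amendment before results are analysed by group. The documents do not say whether outcomes by group have been seen; if they have, the amendment should state what was seen and when.

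- **If 5% was meant**, replace the sentence with, for example: *The primary comparison, [one healing outcome from Tool II] at [one named visit], is tested at the two-sided 5% level (p<0.05). All other comparisons are secondary or exploratory.* Limiting 5% to one comparison matters because of the 26-40% single-visit false-positive chance shown above. As follow-up runs until healing, the amendment should also say how a wound healed before the named visit is counted.
- **If 0.5% was deliberate**, keep it and add: *All tests are two-sided. The 0.5% level (p<0.005) is used because [reason].* Report the lower power alongside: about 1.08 SD detectable with 80% power if the main outcome is continuous and roughly normal, or the matching figure for a categorical outcome.

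**Cost.** No extra patients or data. Keeping 0.5% takes a sentence or two and leaves power at 0.8 SD near 46%. Moving to 5% takes more thought, since a primary outcome and visit must be chosen from a tool with no scoring stated. It raises the primary test's false-positive risk from 0.5% to 5%, and the other comparisons can no longer be read as confirmatory.
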